2 PROTOCOL SYNOPSIS

Title	A Phase 3b Open-label Study Evaluating the Long-term Safety and Efficacy of Elexacaftor/Tezacaftor/Ivacaftor Combination Therapy in Cystic Fibrosis Subjects Ages 6 Years and Older Who Are Heterozygous for the F508del Mutation and a Minimal Function Mutation (F/MF)
Brief Title	A Study Evaluating the Long-term Safety and Efficacy of Elexacaftor/Tezacaftor/Ivacaftor in Cystic Fibrosis (CF) Subjects 6 Years and Older and F/MF genotypes
Clinical Phase and Clinical Study Type	Phase 3b, safety, efficacy
Objectives	
Primary Objective
 
To evaluate the long-term safety and tolerability of elexacaftor (ELX)/tezacaftor (TEZ)/ivacaftor (IVA) in subjects with CF
 
Secondary Objectives
 
 • To evaluate the efficacy of ELX/TEZ/IVA • To evaluate the pharmacodynamics (PD) of ELX/TEZ/IVA
Endpoints	
Primary Endpoint
 
Safety and tolerability of ELX/TEZ/IVA based on adverse events (AEs), clinical laboratory values, ECGs, vital signs, and pulse oximetry
 
Secondary Endpoints
 
 • Absolute change in sweat chloride (SwCl) from baseline • Absolute change in lung clearance index_{2.5} (LCI_{2.5}) from baseline 
Other Endpoints
 
 • Absolute change in percent predicted forced expiratory volume in 1 second (ppFEV₁) from baseline • Absolute change in Cystic Fibrosis Questionnaire-Revised (CFQ-R) respiratory domain score from baseline
Number of Subjects	Subjects who participated in the parent study (VX19-445-116) and meet the eligibility criteria may enroll. Approximately 108 subjects are expected to enroll in this extension study.
Study Population	Male and female CF subjects who are 6 years of age or older who have F/MF genotypes.
Investigational Drug	
Active substance: ELX (VX-445)/TEZ (VX-661)/IVA (VX-770)
 
Activity: CFTR correctors (ELX and TEZ) and potentiator (IVA)
 
Strength and route of administration:
 
 • 50-mg ELX/25-mg TEZ/37.5-mg IVA fixed-dose combination (FDC) tablets for oral administration

- 100-mg ELX/50-mg TEZ/75-mg IVA FDC tablets for oral administration

Active substance: IVA (VX-770)

Activity: CFTR potentiator

[figure not shown]
Strength and route of administration:

- 75-mg IVA tablets for oral administration
- 150-mg IVA tablets for oral administration

Study Duration The total study duration is approximately 100 weeks (from the first dose of study drug in this study), including a Treatment Period of 96 weeks and a 4-week Safety Follow-up Visit.

Study Design This is a Phase 3b, multicenter, open-label study for subjects who complete the parent study (VX19-445-116) and meet eligibility criteria. A schematic of the study design is shown in Figure 2-1.

Figure 2-1 VX20-445-119 Study Design

ELX: elexacaftor; IVA: ivacaftor, TEZ: tezacaftor

Note: Figure not drawn to scale.

Subjects will receive ELX/TEZ/IVA at the weight-appropriate dosage levels shown in Table 2-1 based on their weight at Day 1.

Table 2-1 Treatment Period Dosages

Subject Age Weight	ELX Dosage	TEZ Dosage	IVA Dosage
≥6 to <12 years			
<30 kg	100 mg qd	50 mg qd	75 mg q12h
≥30 kg	200 mg qd	100 mg qd	150 mg q12h
≥12 years			
All weights	200 mg qd	100 mg qd	150 mg q12h

ELX: elexacaftor; IVA: ivacaftor; q12h: every 12 hours; qd: once daily; TEZ: tezacaftor

If a subject enters the current study weighing <30 kg and subsequently weighs ≥30 kg at 2 consecutive clinic visits (excluding unscheduled visits), the dose will be adjusted to the higher dose of ELX 200 mg qd/TEZ 100 mg qd/IVA 150 mg q12h for the remainder of the study, starting with the second visit where the subject’s weight is ≥30 kg.

Subjects ≥12 years of age will receive a dose of ELX 200 mg qd/TEZ 100 mg qd/IVA 150 mg q12h, starting from the first study visit at which the subject is ≥12 years old.

Assessments **Safety:** AEs, clinical laboratory assessments, ECGs, vital signs, height, weight, pulse oximetry, physical examinations (PEs), and ophthalmologic examinations
Efficacy: Multiple-breath washout (MBW), spirometry, and CFQ-R
Pharmacodynamics (PD): SwCl
Other: blood samples for blood biomarker analysis

Statistical Analyses The primary objective of the study is the evaluation of the long-term safety and tolerability of ELX/TEZ/IVA in subjects with CF. The safety endpoints of long-term treatment include AEs, clinical laboratory values, ECGs, vital signs, and pulse oximetry from the first dose of study drug in the open label study, for subjects who have received at least 1 dose of study drug in the open label study. The safety analysis will be descriptive only, and in general will be performed for the pooled population.

The secondary objective of the study is the evaluation of long-term efficacy of ELX/TEZ/IVA, as assessed by SwCl, LCI_{2.5}, spirometry, and CFQ-R. Methods of efficacy analyses will be similar as those used in parent studies

Interim Analyses Interim analyses may take place at any time at the discretion of the sponsor.

DMC Reviews A data monitoring committee (DMC) will conduct periodic safety review(s) of study data as outlined in the DMC charter.

3 SCHEDULE OF ASSESSMENTS

The schedule of assessments is in Table 3-1. All visits will be scheduled relative to the Day 1 Visit in this study.

Assessments may be performed in any order when more than 1 assessment is required at a particular time point, unless noted otherwise. All assessments should be performed before study drug dosing (Section 9.6), unless noted otherwise.

Table 3-1 Study VX20-445-119: Treatment Period and Safety Follow-up Visit								
Event/ Assessment ^a	Treatment Period					ETT Visit ^b	Safety Follow-up Visit (28 ± 7 Days After Last Dose of Study Drug ^c)	Comments
	Day 1 ^d	Weeks 4, 8, 16, 24 (± 5 Days)	Weeks 12, 20, 28, 32, 40, 44, 52, 56, 64, 68, 76, 80, 88, 92 (± 5 Days)	Weeks 36, 48, 60, 72, 84 (± 5 Days)	Week 96 (± 10 Days)			
Clinic visit	X	X		X	X	X	X	See Section 9.1.6 for use of remote measures in extenuating circumstances.
Telephone contact			X					Assess subject's status, any AEs, concomitant medications, treatments, and procedures.
ICF and assent	X							
Safety and Efficacy Assessments								
CFQ-R	X	X		Weeks 48, 72	X			Completed before the start of any other assessments (Section 11.2.4).
Ophthalmologic examination				Week 48 (± 4 weeks)	X (- 4 weeks)	X (- 4 weeks)	X (- 4 weeks)	Subjects will have an ophthalmologic examination at the completion of study participation (defined in Section 9.1.5). This examination should be completed at or up to 4 weeks before the relevant study visit (Section 11.4.6).
Height and weight	X	X		X	X	X	X	Measured with shoes off (Section 11.4.4).
Vital signs and pulse oximetry	X	X		X	X	X	X	Performed after subject has been at rest for at least 5 minutes (Section 11.4.3).
Physical examination (PE)	X				X	X		Symptom-directed PEs may be performed at any time if deemed necessary by the investigator (Section 11.4.3).

^a All assessments will be performed before dosing unless noted otherwise.

^b If the subject prematurely discontinues study drug treatment, an ETT Visit should be scheduled as soon as possible after the decision to discontinue treatment (Section 9.1.3).

^c The Safety Follow-up Visit is required for all subjects, unless otherwise specified. For subjects who complete an ETT Visit 3 weeks or later following the last dose of study drug, the ETT Visit will replace the Safety Follow-up Visit (Section 9.1.2).

^d The Day 1 Visit should be on the same day as the last scheduled visit of the parent study (Section 9.1.1). Subjects whose Day 1 Visit is NOT within 1 day of the last scheduled visit of the parent study will repeat all Day 1 assessments. Subjects whose Day 1 Visit is within 1 day of the last scheduled visit of the parent study will NOT have to repeat any Day 1 assessments that were specified to be performed at the last scheduled visit in the parent study.

Table 3-1 Study VX20-445-119: Treatment Period and Safety Follow-up Visit									
Event/ Assessment ^a	Treatment Period					ETT Visit ^b	Safety Follow-up Visit (28 ± 7 Days After Last Dose of Study Drug ^c)	Comments	
	Day 1 ^d	Weeks 4, 8, 16, 24 (± 5 Days)	Weeks 12, 20, 28, 32, 40, 44, 52, 56, 64, 68, 76, 80, 88, 92 (± 5 Days)	Weeks 36, 48, 60, 72, 84 (± 5 Days)	Week 96 (± 10 Days)				
Standard 12-lead ECG	X	Weeks 8, 16, 24		Weeks 48, 72	X	X	X	Performed prior to any procedure that may affect heart rate (e.g., blood draws) and after subject has been at rest for at least 5 minutes (Section 11.4.5).	
Sweat chloride	X	X		Weeks 48, 72	X	X		Section 11.2.1	
Multiple-breath washout	X	X		Weeks 48, 72	X	X		Performed in multiple replicates, pre-bronchodilator, before the AM dose, and before spirometry assessment (Section 11.2.1).	
Spirometry	X	X		X	X	X	X	Performed pre-bronchodilator, before the AM dose, and at approximately the same time at each visit (Section 11.2.3).	
Pregnancy test	Urine	Serum	Urine	Serum	Serum	Serum	Serum	For all female subjects at telephone contacts, a urine pregnancy test will be performed with a home kit provided by the study site. Results of the home pregnancy test will be reported to the site by telephone (Section 11.4.2).	
Serum chemistry	X	X		X	X	X	X	Section 11.4.2	
Hematology	X	X		X	X	X	X		
Coagulation	X	Week 24		Weeks 48, 72	X	X			
Urinalysis	X			Week 48	X	X			
AEs and SAEs	Continuous from signing of the ICF through completion of study participation								Section 13.1; Completion of study participation is defined in Section 9.1.5.

Table 3-1 Study VX20-445-119: Treatment Period and Safety Follow-up Visit								
Event/ Assessment ^a	Treatment Period					ETT Visit ^b	Safety Follow-up Visit (28 ± 7 Days After Last Dose of Study Drug ^c)	Comments
	Day 1 ^d	Weeks 4, 8, 16, 24 (± 5 Days)	Weeks 12, 20, 28, 32, 40, 44, 52, 56, 64, 68, 76, 80, 88, 92 (± 5 Days)	Weeks 36, 48, 60, 72, 84 (± 5 Days)	Week 96 (± 10 Days)			
Medications review	Continuous from signing of the ICF through completion of study participation							Completion of study participation is defined in Section 9.1.5.
Treatments and procedures review	Continuous from signing of the ICF through completion of study participation							
Biomarker Assessment								
Blood biomarker collection	X	Week 24		Week 48	X	X		Section 11.3.1
Study Drug Administration								
ELX/TEZ/IVA	Day 1 through evening before Week 96 Visit							Subjects on study drug interruption from the parent study may NOT begin dosing until they meet the resumption criteria in Section 9.8. Refer to Section 9.6.1 for study drug administration details.
Study drug count	X	X		X	X	X		

AE: adverse event; CFQ-R: Cystic Fibrosis Questionnaire-Revised; ELX: elxacaftor; ETT: early termination of treatment; ICF: informed consent form; IVA: ivacaftor; PE: physical examination; SAE: serious adverse event; TEZ: tezacaftor

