9.1.3 Early Termination of Treatment

If a subject prematurely discontinues study drug treatment, an ETT Visit should be scheduled as soon as possible after the decision to discontinue treatment.

If the ETT Visit occurs 3 weeks or later following the last dose of study drug, then the ETT Visit will replace the Safety Follow-up Visit.

If a subject withdraws from the study and also withdraws consent or assent, no further assessments will be performed. Vertex may retain and continue to use any data and samples collected before such withdrawal of consent or assent.

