8.3.2.2 Analysis Method

Absolute change in SwCl from baseline:

The mixed-effects model for repeated measures (MMRM) for the parent study 116-FAS will be same as that described in the SAP for Study 116. In the MMRM for the OL-FAS, the absolute change from baseline in SwCl will be the dependent variable. The model will include treatment group (as randomized in the parent study), visit, and treatment-by-visit interaction as fixed effects, with continuous baseline LCI_{2.5} from the parent study and weight at Screening (<30 versus ≥30 kg) of the parent study as covariates.

The repeated-measures analysis will be based on the restricted maximum likelihood method assuming an unstructured covariance structure to model the within-subject errors. The denominator degrees of freedom will be based on the method proposed by Kenward-Roger⁶. If the model fails to converge due to the unstructured covariance assumption, a compound symmetry covariance structure will be used to model the within-subject errors. In the MMRM approach, assuming that the data are missing at random, no imputation of missing data will be performed.

Results from the 2 MMRMs (for the parent study and for the OE) will be presented in a single summary table. The number of subjects, least-squares means (LS means) for absolute change from baseline at scheduled visits within each treatment group (as randomized in the parent study) along with the corresponding standard error (SE), and 95% confidence interval (CI) will be presented. The LS means (±SE) for absolute change from baseline at each visit will also be plotted by treatment group (as randomized in the parent study).

In addition, the descriptive statistics for raw values and absolute changes from baseline by treatment group (as randomized in the parent study) and OL visit will be presented for the OL-FAS.

Absolute change in LCI_{2.5} from baseline:

Analysis of this endpoint will be based on an MMRM similar to the analysis of the absolute change from baseline in SwCl. A descriptive summary of raw values and absolute changes from baseline will also be presented.

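### CFQ-R is the only efficacy or PD measure not scheduled at the Early Termination of Treatment (ETT) Visit, so a subject who stops after Week 24 can leave with a last score up to 24 weeks old

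*Protocol*

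**What the plan says.** Four measures serve the efficacy and PD objectives: sweat chloride (SwCl), LCI2.5, spirometry and CFQ-R (Protocol synopsis, Statistical Analyses). Their rows in Protocol Table 3-1, with empty cells closed up, read:

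- "CFQ-R X X Weeks 48, 72 X Completed before the start of any other assessments (Section 11.2.4"
- "Sweat chloride X X Weeks 48, 72 X X Section 11.2.1"
- "Multiple-breath washout X X Weeks 48, 72 X X"
- "Spirometry X X X X X X"

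Set against the column headings, the last CFQ-R entry before the comment ("Completed before the start of any other assessments (Section 11.2.4") is Week 96, and its ETT and Safety Follow-up cells are empty. SwCl and multiple-breath washout (MBW) have one further mark, at ETT. Spirometry is marked at ETT and at Safety Follow-up.

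For a subject who stops early, Protocol Section 9.1.3 says that "an ETT Visit should be scheduled as soon as possible after the decision to discontinue treatment". It sets no maximum delay. Section 9.9 says that such subjects continue to be followed, but the only visits laid out for them are ETT and Safety Follow-up. Section 11.2.4 (CFQ-R) adds no ETT assessment, and neither does the SAP. No reason for the omission is given.

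SAP Section 8.3.3.2 analyses the CFQ-R respiratory domain with an MMRM similar to that for SwCl. For that model SAP Section 8.3.2.2 states: "assuming that the data are missing at random, no imputation of missing data will be performed". SAP Appendix A gives SwCl, LCI2.5 and CFQ-R one common set of analysis windows.

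**The concern.** CFQ-R is the only patient-reported endpoint, and it is the one measure with no exit value. After Week 24 it is collected every 24 weeks, so the state of a subject shortly before stopping may never be recorded. Missing at random is easiest to defend when the last observed score is recent. If symptoms decline between the last scheduled questionnaire and the stop, by more than the earlier scores would predict, the model has no sight of the decline. The later CFQ-R LS means would then be too favourable.

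The contrast with SwCl and LCI2.5 is what makes the gap look unintended. They share CFQ-R's treatment visits and analysis windows, yet they are collected at ETT. Burden does not explain it: MBW, which Protocol Section 9.1.6 does not allow at home visits, is required at ETT, while a questionnaire is not.

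**Working it through.** The documents state no figure for this gap, so there is none to reproduce.

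**1. Gap between scheduled CFQ-R assessments.** Inputs: visit weeks and windows from Protocol Table 3-1 (±5 days through Week 84, ±10 days at Week 96). The longest gap is the nominal gap in days plus the windows at both ends.

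| Interval | Nominal gap | Longest gap with windows |
|---|---|---|
| Day 1 to Week 4 | 4 weeks | 28 + 5 = 33 days |
| Week 4 to 8 | 4 weeks | 28 + 5 + 5 = 38 days |
| Week 8 to 16 | 8 weeks | 56 + 5 + 5 = 66 days (9.4 weeks) |
| Week 16 to 24 | 8 weeks | 66 days (9.4 weeks) |
| Week 24 to 48 | 24 weeks | 168 + 5 + 5 = 178 days (25.4 weeks) |
| Week 48 to 72 | 24 weeks | 178 days (25.4 weeks) |
| Week 72 to 96 | 24 weeks | 168 + 5 + 10 = 183 days (26.1 weeks) |

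**2. Mean age of the last score at stopping.** If stopping is uniform within an interval of length L, the mean gap is L/2. After Week 24 that is 24/2 = 12 weeks. If stopping is uniform over all 96 weeks, the mean is ΣL²/(2 × 96) = (2 × 4² + 2 × 8² + 3 × 24²)/192 = (32 + 128 + 1728)/192 = 1888/192 = 9.8 weeks.

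**3. When an ETT score would enter the MMRM.** Inputs: the SAP Appendix A windows for SwCl, LCI2.5 and CFQ-R after Week 24, which are (141, 253] for Week 24 (target day 169), (253, 421] for Week 48 (337), (421, 589] for Week 72 (505) and (589, 729] for Week 96 (673). When several values fall in one window, the one closest to the target day is used. Assume scheduled visits fall on target days.

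- ETT on days 170 to 253: the window already holds the Week 24 score on target, so the ETT score is not used at a visit.
- ETT on days 254 to 336: the Week 48 window is otherwise empty, so the ETT score fills it (83 days).
- The same pattern gives days 422 to 504 for Week 72 (83 days) and days 590 to 672 for Week 96 (83 days).

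Between Week 24 and Week 96 there are 3 × 167 = 501 days strictly between target days, and an ETT score enters on 3 × 83 = 249 of them: 249/501 = 50%. The four windows up to Week 24 add 27 + 13 + 27 + 27 = 94 days, so over days 2 to 672 the share is 343/671 = 51%. The days on which the score enters are those furthest from the previous questionnaire: day 254 is 85 days after day 169.

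**4. Number affected.** The documents give about 108 expected subjects and no discontinuation rate. Assuming 5% to 20% stop early, 0.05 × 108 = 5.4 and 0.20 × 108 = 21.6, so about 5 to 22 subjects would have no exit score. If stops were spread evenly, 51% of these, or about 3 to 11 (0.51 × 5.4 = 2.8; 0.51 × 21.6 = 11.0), would have an ETT score used in the model.

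**The case against.** The omission contradicts nothing else in the documents, and it may have been deliberate. The parent study's schedule, which might explain it, is not available. CFQ-R is listed under Other Endpoints in a study whose primary objective is safety, and adverse events leading to discontinuation are captured regardless. All of this stands, and it limits the importance of the point.

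Three stronger readings are tempting, and the documents do not support them.

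- *The omission biases CFQ-R in favour of the drug.* The MMRM carries no old score forward; missing visits are handled under missing at random. Bias requires a decline before stopping that earlier scores do not predict. Not every early exit implies decline: Protocol Section 9.1.2 provides for transition to a commercial, managed-access or other study regimen before Week 96.
- *An ETT score would always be used.* Under the closest-to-target rule it would be used on only about half of possible days after Week 24.
- *The other endpoints show the decline that CFQ-R misses.* SwCl and LCI2.5 share the CFQ-R windows, so their ETT values also drop out of the visit-based analysis about half the time. Protocol Section 11.2.1 describes SwCl as a biomarker of CFTR activity; it is not a symptom measure.

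A further objection is that an ETT score may be taken off drug, possibly 3 weeks or more after the last dose, and then assigned to a later analysis visit. That is true, but the plan already accepts it for SwCl, LCI2.5 and spirometry, so collecting CFQ-R raises no new question of principle.

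**Conclusion.** The point holds as a cheap improvement to the schedule. CFQ-R is the only one of the four efficacy and PD measures without an ETT assessment, and nothing elsewhere in the protocol or SAP supplies one. The last score can be up to 24 weeks old for a stop after Week 24 (about 25 to 26 weeks with windows). For a stop before Week 24 it is at most 8 weeks old nominally (9.4 weeks with windows). The 9.8-week mean rests on uniform stopping over 96 weeks, and the 5 to 22 subjects rest on an assumed 5% to 20% rate.

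Whether later CFQ-R LS means are in fact too favourable cannot be told from the documents. It depends on unobserved worsening before the stop and on how many subjects stop. No safety conclusion is affected.

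**What to change.** Add an X for CFQ-R in the ETT column of Table 3-1, completed before the other assessments as at every other visit. The existing SAP windows and closest-to-target rule can stay. The SAP could state that an ETT score enters the MMRM only when its window is otherwise empty, and is otherwise kept for listings and descriptive summaries.

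The cost is one table cell in a protocol amendment and a few minutes of the subject's time at a clinic visit already attended. Some scores will be taken off drug, since the ETT Visit has no maximum delay; this is already so for the other three measures. If the schedule is not changed, give the reason and note the missing exit score as a limitation when CFQ-R is reported.

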Table 13-2	Classifications for AE Causality.....	43
Table 13-3	Classifications for Study Drug Action Taken With Regard to an AE	43
Table 13-4	Classifications for Outcome of an AE	44

List of Figures

Figure 2-1	VX20-445-119 Study Design	3
Figure 9-1	VX20-445-119 Study Design	18

List of Abbreviations

Abbreviation	Definition
ADL	activities of daily living
AEs	adverse events
ALT	alanine transaminase
AST	aspartate transaminase
β	beta, apparent elimination rate constant
BMI	body mass index
CD	compact disc
CF	Cystic Fibrosis
CFQ-R	Cystic Fibrosis Questionnaire-Revised
CFTR	CF transmembrane conductance regulator gene
CI	confidence interval
COVID-19	coronavirus disease
CRF	case report form
CSR	clinical study report
CTCAE	Common Terminology Criteria for Adverse Events
CYP	cytochrome P450
DMC	data monitoring committee
ECG	electrocardiogram
EDC	electronic data capture
EENT	eyes, ears, nose, and throat
ELX	elexacaftor
ETT	Early Termination of Treatment
EU	European Union
F/MF	F508del Mutation and a Minimal Function Mutation
F508del	CFTR gene mutation with an in-frame deletion of a phenylalanine codon corresponding to position 508 of the wild-type protein
FDA	Food and Drug Administration
FDC	fixed-dose combination
FEF _{25%-75%}	forced expiratory flow, midexpiratory phase
FEV ₁	forced expiratory volume in 1 second
FSH	follicle-stimulating hormone
FVC	Forced vital capacity
GCP	Good Clinical Practice
GLI	Global Lung Function Initiative
GPP3	Good Publishing Practices

Abbreviation	Definition
GPS	Global Patient Safety
HIPAA	Health Insurance Portability and Accountability Act
HR	heart rate
ICF	informed consent form
ICH	International Council for Harmonization
ICMJE	International Committee of Medical Journal Editors
IEC	independent ethics committee
IMP	investigational medicinal product
IPD	important protocol deviation
IRB	institutional review board
IVA	ivacaftor
IWRS	interactive web response system
LCI	lung clearance index
LCI _{2.5}	number of lung turnovers required to reduce the end tidal inert gas concentration to 1/40th of its starting value
LS	least squares
LUM	lumacaftor
max	maximum value
MBW	Multiple-breath washout
MedDRA	Medical Dictionary for Regulatory Activities
min	minimum value
MMRM	mixed-effects model for repeated measures
N	total sample size
OATP1B1	organic anion transporting polypeptide 1B1
OATP1B3	organic anion transporting polypeptide 1B3
OL-FAS	Open-label Full Analysis Set
OL-SS	Open-label Safety Set
PC	publication committee
PD	pharmacodynamics
PEs	physical examinations
P-gp	P-glycoprotein
PIs	principal investigators
ppFEV ₁	percent predicted forced expiratory volume in 1 second
PR	PR interval, segment
PT	Preferred Term
q12h	every 12 hours

Abbreviation	Definition
qd	once daily
QRS	the portion of an ECG comprising the Q, R, and S waves, together representing ventricular depolarization
QT	QT interval
QTcF	QT interval corrected by Fridericia's formula
RNA	ribonucleic acid
RR	interval from the onset of 1 QRS complex to the next; use R-R if using with "intervals", i.e., "R-R interval"
SAE	serious adverse event
SAP	statistical analysis plan
SC	steering committee
SD	standard deviation
SET	Study Execution Team
SI	SI units (International System of Units)
SOC	System Organ Class
SUSARs	serious adverse reactions
SwCl	sweat chloride
TE	Treatment-emergent
TEAEs	treatment-emergent adverse events
TEZ	tezacaftor
ULN	upper limit of normal
US	United States
USA	United States of America
VAS	visual analog scale

